## **Exploratory Analyses**

We will examine whether participant characteristics (i.e., gender, age, race/ethnicity, and perceived weight status) moderate the effect of label type (compared to control) on the primary outcome. If the main analysis (model 1) reveals that there is no significant interaction by label type and label version, we will fit a series of mixed-effects models with random intercepts (one for each potential moderator) including label type, label version, the moderator, two-way interactions between label type and label version, and two-way interactions between label type and the moderator. If, in turn, the main analysis (model 1) reveals a significant interaction by label type and label version, we will run separate moderation models for regular labels and for modified labels. We will consider moderation to be supported if the interaction terms between label types and the moderator (in either scenario) are statistically significant, and we will probe such significant interactions by calculating the marginal effect of label types on the outcome at different levels of the moderating variables. We will use Wald tests for categorical moderators with more than 2 categories.

## **Sample Size and Power**

This study will occur in a survey that will follow a parent experiment about alcohol messages. The total sample size (~2,500 participants) was calculated based on the primary outcomes of the parent experiment.

Using G\*Power3.1 and specifying a between-within subjects ANOVA (which should most closely approximate the proposed mixed linear model), we determined the

minimum effect size we would be able to detect on our primary outcome with this pre-determined sample size. With 80% power, a critical alpha of 0.05, four conditions, and two repeated measures, we would be able to detect an effect of  $f=0.057$  (equivalent to  $d=0.11$ ) or larger for the between-subjects factor, and  $f=0.028$  (equivalent to  $d=0.06$ ) or larger for the within-subjects factor. Given that a previous study to analyze the effect of FOPLs on perceived weight stigmatization obtained an effect size of  $d=0.25$  comparing nutrient warnings to control, this study's sample should be sufficiently large to detect an even smaller effect when comparing between nutrient warnings and text-only health warnings, which we expect to be the smallest effect.

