## Hypotheses

Primary outcome: We hypothesize that graphic health warnings will be perceived as most stigmatizing, followed respectively by text-only health warnings, nutrient warnings, and control labels (H1). We also hypothesize that, for all label types, the modified version will be perceived as less stigmatizing than the regular version of the same label (H2).

Secondary outcomes: We hypothesize that graphic health warnings will be perceived as most effective, followed respectively by text-only health warnings, nutrient warnings, and control labels (H3). We also hypothesize that graphic health warnings will elicit the most weight bias, followed respectively by text-only health warnings, nutrient warnings, and control labels (H4).

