## Main Analyses

We will use a two-sided critical alpha of 0.05 to conduct all statistical tests. All confidence intervals presented will use a 95% confidence level. Analyses of the primary and secondary outcomes will include all participants according to the trial arm to which they were randomized. We will use complete case analysis to handle any missing data.

To prepare the data, we will verify that Cronbach's alpha for all scales is sufficient ( $\geq 0.7$ ) and, if so, we will average items to create a mean score on each scale for each

participant. If Cronbach's alpha is not sufficient (<0.7), we will drop items as necessary to improve reliability or treat items as separate constructs.

We will first descriptively report unadjusted means for the primary and secondary outcomes for each experimental arm. To test H1 and H2 (model 1) and H3 (model 2), we will fit separate mixed-effects models with random intercepts to account for repeated measures within participants. These models will include indicator variables for label type (i.e., nutrients, text-only, and graphic - the control label type will be omitted as the referent group), an indicator variable for label version (i.e., regular vs. modified), and interaction terms between label type and label version (i.e., nutrients\*modified, text-only\*modified, and graphic\*modified). To test H4 (model 3), we will fit a linear model including only indicators for label type.

If the interaction terms in models 1 and 2 are not significant, after fitting models 1-3, we will use these models to estimate the main average differential effects of label types (i.e., differences in predicted means between label types averaging between the two version of each label). We will obtain the effect of each label type vs. control, as well as of nutrient vs. text-only, text-only vs. graphic, and nutrient vs. graphic label types. If, in turn, the interaction terms in models 1 and 2 are significant, after fitting models 1 and 2, we will estimate the average differential effects of label types and report them separately for each version of the labels (i.e., we will present differences by label type separately for regular labels and for modified labels). We will not adjust the p-value for each label type compared to control, but will adjust for multiple tests for the three additional pairwise comparisons using the Bonferroni-Holm correction.

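### The stated detectable d of 0.11 is converted from a four-group omnibus test; the planned pairwise label contrasts can detect about 0.14, or 0.16 within one label version

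*Combined protocol and SAP*

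**What the plan says.** Sample Size and Power takes the total of about 2,500 from the parent experiment and works back to a detectable effect, using G*Power's between-within ANOVA as an approximation to the mixed model. With 80% power, alpha 0.05, four conditions and two repeated measures, it gives f=0.057 (d=0.11) "or larger for the between-subjects factor", and f=0.028 (d=0.06) for the within-subjects factor. It then cites a previous study's d=0.25 for nutrient warnings against control and concludes that "this study's sample should be sufficiently large to detect an even smaller effect when comparing between nutrient warnings and text-only health warnings", adding of that contrast, "which we expect to be the smallest effect".

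Main Analyses describes the tests to be run: "We will obtain the effect of each label type vs. control, as well as of nutrient vs. text-only, text-only vs. graphic", and nutrient vs graphic. These are averaged over the two versions if the label-by-version interaction is not significant. If it is, "we will present differences by label type separately for regular labels and for modified labels". The contrasts against control are unadjusted; for the rest the plan will "adjust for multiple tests for the three additional pairwise comparisons using the Bonferroni-Holm correction".

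**The concern.** The power statement and the planned analysis refer to different tests. A between-subjects factor with four levels is tested on 3 degrees of freedom, and its f describes the spread of all four means. The analysis plans no such test of label type; it compares label types two at a time. The plan turns the omnibus f into a d, sets it beside a two-group d from an earlier study, and draws a conclusion about a single two-group contrast. A reader will therefore take 0.11 as the pairwise difference the study has 80% power to detect.

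This matters most for nutrient vs text-only, which the plan expects to be the smallest effect but for which it gives no expected size. A null result there would be read against 0.11, as though a difference of that size would have been found four times in five.

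**Working it through.** **Inputs.** From Sample Size and Power: N about 2,500, 80% power, four conditions, two repeated measures. From Main Analyses: two-sided alpha 0.05, and Holm over three contrasts. Assumed: equal allocation, so 2,500/4 = 625 per arm (Study Protocol gives no ratio), all analysed; d in units of the SD of a single rating. The within-person correlation ρ is not stated and is recovered in step 1.

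**1. Reproduce the plan's f values.** For 80% power at alpha 0.05 the noncentrality must be 10.92 for F(3, 2496) and 7.855 for F(1, 2496).

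- Label type: λ = f²·N·2/(1+ρ). At ρ=0.5, f = √(10.92 × 1.5/5000) = 0.0572.
- Version, pooled over label types: λ = f²·N·2/(1−ρ). At ρ=0.5, f = √(7.855 × 0.5/5000) = 0.0280.

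| ρ | f, label type | f, version |
|---|---|---|
| 0 | 0.0467 | 0.0396 |
| 0.3 | 0.0533 | 0.0332 |
| 0.5 | 0.0572 | 0.0280 |
| 0.7 | 0.0609 | 0.0217 |
| 0.9 | 0.0644 | 0.0125 |

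Of these, only ρ=0.5 returns both stated values. Allowing for rounding, f=0.057 back-solves to ρ of about 0.46 to 0.51 and f=0.028 to about 0.48 to 0.52.

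**2. What d=0.11 is.** 2 × 0.057 = 0.114. With four equal arms, f is the SD of the four means in rating-SD units. It equals half the largest difference only if two arms sit at one extreme and two at the other. As an illustration, four equally spaced means in H1's order have SD √1.25 times the step, so f=0.057 means an end-to-end d of 3 × 0.057/√1.25 = 0.153.

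**3. Detectable pairwise d.** Standard error of a two-arm contrast in d units:

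- averaged over versions: √[(2/625)(1+ρ)/2] = 0.0490 at ρ=0.5
- within one version: √(2/625) = 0.0566, whatever ρ is

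Detectable d = (z for the alpha level + 0.842) × SE:

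| Two-sided alpha | Averaged, ρ=0.5 | One version |
|---|---|---|
| 0.05 | 0.137 | 0.158 |
| 0.025 | 0.151 | 0.174 |
| 0.0167 (first Holm step) | 0.159 | 0.183 |

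At alpha 0.05 the averaged figure runs from 0.128 (ρ=0.3) to 0.154 (ρ=0.9). It comes down to 0.112 only at ρ=0, where the omnibus f would be 0.047 rather than the stated 0.057.

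**4. Power at d=0.11, alpha 0.05.** Power = Φ(d/SE − 1.96).

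- averaged: Φ(0.11/0.0490 − 1.96) = 61% (67% at ρ=0.3, 51% at ρ=0.9)
- one version: Φ(0.11/0.0566 − 1.96) = 49%

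For 80% power at d=0.11 the SE would have to be 0.11/2.802 = 0.03926. That needs 1.5/0.03926² ≈ 973 per arm averaged, or 2/0.03926² ≈ 1,297 within one version.

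**5. Nutrient vs text-only under Holm.** The full procedure was simulated (1,000,000 draws per setting, ρ=0.5) with nutrient vs text-only at d=0.11 and text-only vs graphic at an assumed d of 0.11 to 0.30. Nutrient vs text-only was tested first in at most 1.2% of runs averaged and 2.6% within one version. Its power was 56% to 61% and 42% to 49%. Solving for 80% power, with the text-only vs graphic gap at 1, 1.5 and 2 times the nutrient vs text-only gap, gives d of 0.137 to 0.139 averaged and 0.158 to 0.161 within one version.

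**6. The benchmark.** At d=0.25, power is at least 97.9%, the lowest case being one version at the first Holm step.

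**The case against.** The conversion is correctly multiplied, and d=2f is a common convention. The plan attaches 0.11 to the factor of a four-condition ANOVA, which it presents as an approximation, and never says in terms that 0.11 applies to two arms. Its conclusion is only that something smaller than 0.25 can be detected, which is true. No test, estimate or decision rule uses 0.11, and nobody has proposed 0.11 as the true nutrient vs text-only difference.

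Most of that stands as a limit on the consequence. It does not rescue the figure: d=2f is exact for two equal groups, there are four here, and the next sentence uses the result for a two-group contrast. Because that contrast has no expected size, the lower limit of detectability is what the reader needs, and the only one offered is too small.

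Three narrower objections are fair:

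- Equal spacing in step 2 is only an illustration. H1 gives an order, and the plan expects one gap to be smallest.
- The figures assume no losses, while Main Analyses specifies complete-case analysis. If 10% were lost (an assumed figure), 0.137 and 0.158 would become about 0.145 and 0.167; at 20%, about 0.153 and 0.177.
- H2 is stated for every label type, whereas d=0.06 is for the version effect pooled over them. Within one label type the detectable version difference is 2.802 × √[2(1−0.5)/625] = 0.112 at ρ=0.5. Labelling 0.06 as pooled makes it accurate.

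**Conclusion.** The concern holds. The f values are right for the tests they describe, but d=0.11 is not what the planned label-type contrasts can detect with 80% power. Under the stated assumptions the figure is about 0.14 averaged over versions and 0.16 within one version, rising to 0.16 and 0.18 if a contrast must pass the first Holm step. Unequal arms or missing data would tend to raise these figures. The correlation is the plan's own by implication, since both of its f values point to 0.5.

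The error should be corrected but does not threaten the design: the claim that an effect below 0.25 is detectable survives.

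**What to change.** In Sample Size and Power:

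1. State the assumed within-person correlation (0.5 reproduces the figures). Label f=0.057 as the omnibus label-type effect, and f=0.028 (d=0.06) as the version effect pooled over label types.
2. Remove the equivalence to d=0.11 and put in its place: *Assuming equal allocation (about 625 analysed per label type), a within-person correlation of 0.5 and d in single-rating SD units, 80% power corresponds to a pairwise d of about 0.14 averaged over versions (0.13 to 0.15 for correlations 0.3 to 0.9) or 0.16 within one version at alpha 0.05, and up to 0.16 (0.18 within one version) at the first Holm step.*
3. Replace the inference from d=0.25 with: *Nutrient vs text-only, expected to be the smallest effect, would usually be tested at a later Holm step; under the same assumptions its detectable d is about 0.14 averaged over versions and 0.16 within one version.*

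The cost is a few sentences and a slightly less favourable stated sensitivity. Sample size, models and alpha are unchanged.

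### The stated 80% power at f=0.057 (d=0.11) belongs to an any-difference ANOVA test, not to the pairwise contrasts that evaluate H1; one such contrast has about 61% power at d=0.11, and no power is given for the ordering

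*Combined protocol and SAP*

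**What the plan says.** The Hypotheses section states the primary prediction as a full order: "graphic health warnings will be perceived as most stigmatizing, followed respectively by text-only health warnings, nutrient warnings, and control labels (H1". The Main Analyses section tests at a two-sided 0.05 level and answers H1 with six contrasts: "We will obtain the effect of each label type vs. control, as well as of nutrient vs. text-only, text-only vs. graphic, and nutrient vs. graphic". On multiplicity it says "We will not adjust the p-value for each label type compared to control", and that it "will adjust for multiple tests for the three additional pairwise comparisons using the Bonferroni-Holm correction". It does not say which of these results must be significant for H1 to count as supported. The Exploratory Analyses section does give such a rule for moderation.

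The Sample Size and Power section explains that "The total sample size (~2,500 participants) was calculated based on the primary outcomes of the parent experiment". It then works back to a detectable effect: 80% power, four conditions, two repeated measures, f=0.057 (equated with d=0.11) for the between-subjects factor. It cites a previous d=0.25 for nutrient warnings against control, expects nutrient against text-only to be the smallest effect, gives no size for that effect, and concludes that "this study's sample should be sufficiently large to detect an even smaller effect when comparing between nutrient warnings and text-only health warnings".

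**The concern.** A between-subjects ANOVA factor with four levels is tested on 3 degrees of freedom. It can reject when only one label type differs from the rest, so its power is not the power of any particular contrast, still less of a sequence of them. Because d=0.11 is printed beside a pairwise d=0.25, a reader will take it as a pairwise difference that the trial can detect with 80% power.

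At stake is how the primary result is read. If the nutrient against text-only contrast is non-significant, the reader needs to know whether the design had a good chance of showing a step of the expected size. Without a stated rule for H1, partial support could also be reported as support for the whole order.

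**Working it through.** **Inputs.** From the plan: N about 2,500, four arms, two ratings per person, two-sided alpha 0.05, Holm on the three between-warning contrasts, d=0.25 for nutrient against control. Assumed: equal allocation (625 per arm) and a within-person correlation rho of 0.5, with 0.3 to 1.0 as the range. The plan prints neither, but rho=0.5 reproduces both of its f values. Differences are in SD units of a single rating.

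**1. The plan's own figure.** Between factor: lambda = f² × N × 2 / (1 + rho) = 0.057² × 5000 / 1.5 = 10.83. On 3 and 2496 df, power is 79.6%. For exactly 80%, lambda = 10.92 and f = √(10.92 × 1.5 / 5000) = 0.0572. Within factor: lambda = 0.028² × 5000 / 0.5 = 7.84, power 79.9%. Both printed f values are reproduced, and the between-subjects one is the 3-df any-difference test.

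**2. What f=0.057 means for a pairwise difference.** The answer depends on the pattern of means:
- two arms high and two low: 2 × 0.057 = 0.114
- two extreme arms, the others midway: 0.057 × √8 = 0.161 between the extremes
- four equally spaced means: 0.057 / √1.25 = 0.051 per step

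The printed 0.11 fits only the first pattern, which is not the order that H1 predicts.

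**3. One contrast, averaged over versions.** SE = √[((1 + rho)/2) × 2/625]. At rho=0.5 this is √(0.75 × 2/625) = 0.0490. Power at d=0.11 is Φ(0.11/0.0490 − 1.96) = Φ(0.285) = 61%. The difference needed for 80% is (1.96 + 0.8416) × SE.

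| rho | SE | Power at 0.11, unadjusted | Nutrient vs text-only under Holm, equal steps of 0.11 | d for 80%, unadjusted |
|---|---|---|---|---|
| 0.3 | 0.0456 | 67% | 64% | 0.128 |
| 0.5 | 0.0490 | 61% | 56% | 0.137 |
| 1.0 | 0.0566 | 49% | 42% | 0.158 |

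The last row also describes a single label version. It therefore applies if the type-by-version interaction is significant and contrasts are reported version by version.

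**4. All three adjacent steps.** I simulated 600,000 sets of four arm means. Success meant nutrient against control with z>1.96, and both upper steps Holm-significant in a family of three, all in the predicted direction. Steps run control–nutrient / nutrient–text-only / text-only–graphic.

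| Steps | rho 0.3 | rho 0.5 | rho 1.0 |
|---|---|---|---|
| 0.11 / 0.11 / 0.11 | 20% | 12% | 3% |
| 0.137 / 0.137 / 0.137 | 58% | 45% | 21% |
| 0.17 / 0.17 / 0.17 | 89% | 81% | 58% |
| 0.25 / 0.11 / 0.11 | 38% | 29% | 14% |
| 0.25 / 0.11 / 0.25 | 67% | 61% | 48% |
| 0.25 / 0.14 / 0.25 | 87% | 81% | 68% |

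With equal steps, joint power falls below the product of the single powers (at 0.11 and rho 0.5: 0.61 × 0.56 × 0.56 = 0.19, against 0.12). Adjacent contrasts share an arm, so their errors have correlation −0.5. Holm adds little: without it, the 12% becomes 13%.

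**The case against.** The other side has four good arguments.

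- **No written conjunction.** A reader might infer that the plan requires every step to be significant and so has only 12% power for H1. The Main Analyses section lists contrasts and an adjustment, but no such rule. The conjunction is an interpretation of H1, though a natural one.
- **Equal steps of 0.11 are not the plan's scenario.** It cites 0.25 for the first step and expects nutrient against text-only to be the smallest. If both outer steps are large, joint power is almost the power of the smallest step, so checking the smallest expected contrast is a sensible approach. The text-only to graphic step is not given; 0.25 for it is an assumption.
- **The adequacy sentence is not false as worded.** It claims only that something smaller than 0.25 is detectable for nutrient against text-only, and that holds down to about 0.14 to 0.16 unadjusted.
- **No value of rho is printed.** The results move materially with it.

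All four stand, and they limit the point. They do not supply the missing figure: even on the favourable pattern with a middle step of 0.11, ordering power is 61% at rho=0.5, and a single contrast of 0.11 falls short of 80% throughout the range shown.

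**Conclusion.** The point holds in a limited form. The printed f values are correct for the tests they describe. The fault is that the 80% figure belongs to an any-difference test, while H1 is judged on pairwise contrasts for which no power is given. At the printed d=0.11, one unadjusted contrast has about 61% power (49% to 67% for rho 1.0 to 0.3), and nutrient against text-only under Holm with equal steps has 42% to 64%. The pairwise difference with 80% power is about 0.137 (0.128 to 0.158).

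Power for the full order cannot be put as one number. At rho=0.5 it runs from 12% to 81% over the patterns shown. A reader might infer that every step must reach 0.17 for 80% power. That is only the equal-step value at rho=0.5, since 0.25/0.14/0.25 also gives 81%. Nor do the documents show that the trial is likely to miss the order, because they give no size for the two upper steps. All of this assumes 625 per arm and no loss to missing data.

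**What to change.** **Sample Size and Power.**
- State that f=0.057 is for the any-difference test, and drop d=0.11 as a pairwise detectable difference.
- Give the pairwise figure instead: about 0.14 at a within-person correlation of 0.5, rising to about 0.16 at 1.0 or within a single label version.
- Limit the adequacy sentence to differences of that size.
- Add a short table of ordering power over stated step patterns and correlations, such as the one above. Label 0.17 as the equal-step value at correlation 0.5, not as a necessary threshold.
- State the allocation ratio and the correlation assumed.

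**Main Analyses.** Add that the full order in H1 will be claimed only if all three adjacent contrasts are significant in the predicted direction, and that otherwise only the significant steps will be claimed.

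**Cost.** A few sentences and one table, written before data collection, with no extra participants. The price is a less favourable stated detectable difference.

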### **Interim Analysis**

No interim analyses are planned.
